4.2 Scientific Rationale for Study Design

At present, there is no specific antiviral therapy for coronavirus infections. Few treatment studies have been conducted because most human coronavirus strains cause self-limited disease and care

is supportive. After the SARS-CoV was identified in 2002-2003 and caused a large global outbreak, there was an increased interest in the development of specific therapeutic agents. SARS-CoV patients were treated with corticosteroids, type 1 IFN agents, convalescent plasma, ribavirin, and lopinavir or ritonavir, and except for ribavirin, many of these agents have in vitro pre-clinical data that support their efficacy (13-28). Since the SARS-CoV outbreak in 2002-2003, new therapeutic agents targeting viral entry proteins, proteases, polymerases, and methyltransferases have been tested; however, none of them has been shown to be efficacious in clinical trials (29-31).

This study utilizes an adaptive design that increases efficiency to identify safe and efficacious therapeutic agents for patients with COVID-19 during the current outbreak. Some investigational products may be in limited supply and this study design enables continuation of the study even if a product becomes unavailable. In addition, the adaptive design allows for the evaluation of new therapeutic agents as they are identified and ready for testing in clinical trials. As the study is a multicenter, multinational randomized controlled study, we will be able to acquire rigorous data about the safety and efficacy of investigational therapeutic agents for COVID-19 that will lead to generalizable evidence. Randomization is essential for establishing efficacy of these new therapeutic agents. Last, collecting clinical and virologic data on enrolled subjects using a standardized timeline and collection instruments should provide valuable information about the clinical course of and morbidities associated with COVID-19 in a diverse group of hospitalized adults.

4.3 Justification for Dose

The dose of remdesivir used in this study will be the same dose that was used in the Ebola clinical trials.

5. STUDY POPULATION

Approximately 572 male and non-pregnant female adults ≥ 18 years of age or older with COVID-19 and who meet all eligibility criteria will be enrolled at up to approximately 100 clinical trial sites globally. The target population should reflect the community at large. The estimated time from screening (Day -1 or Day 1) to end of study for an individual subject is approximately 29 days.

Subject Inclusion and Exclusion Criteria must be confirmed by any clinician named on the delegation log. If there is any uncertainty, the PI should make the decision on whether a potential subject is eligible for study enrollment. There is no exclusion for receipt of SARS-CoV-2 vaccine (experimental or licensed).

5.1 Inclusion Criteria

In order to be eligible to participate in this study, a patient must meet all of the following criteria:

1. Admitted to a hospital with symptoms suggestive of COVID-19 infection.
2. Subject (or legally authorized representative) provides informed consent prior to initiation of any study procedures.

3. Subject (or legally authorized representative) understands and agrees to comply with planned study procedures.
4. Male or non-pregnant female adult ≥ 18 years of age at time of enrollment.
5. Has laboratory-confirmed SARS-CoV-2 infection as determined by PCR or other commercial or public health assay in any specimen, as documented by either of the following:
 - PCR positive in sample collected < 72 hours prior to randomization; OR
 - PCR positive in sample collected ≥ 72 hours prior to randomization, documented inability to obtain a repeat sample (e.g. due to lack of testing supplies, limited testing capacity, results taking > 24 hours, etc.). AND progressive disease suggestive of ongoing SARS-CoV-2 infection.
6. Illness of any duration, and at least one of the following:
 - Radiographic infiltrates by imaging (chest x-ray, CT scan, etc.), OR
 - SpO₂ $\leq 94\%$ on room air, OR
 - Requiring supplemental oxygen, OR
 - Requiring mechanical ventilation.
7. Women of childbearing potential must agree to either abstinence or use at least one primary form of contraception not including hormonal contraception from the time of screening through Day 29.
8. Agrees to not participate in another clinical trial for the treatment of COVID-19 or SARS-CoV-2 through Day 29.

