3. OBJECTIVES AND ENDPOINTS

The overall objective of the study is to evaluate the clinical efficacy and safety of different investigational therapeutics relative to the control arm among hospitalized adults who have COVID-19.

OBJECTIVES	ENDPOINTS (OUTCOME MEASURES)
Primary	

To evaluate the clinical efficacy, as assessed by time to recovery, of different investigational therapeutics as compared to the control arm.
	
Day of recovery is defined as the first day on which the subject satisfies one of the following three categories from the ordinal scale:
 
 • Hospitalized, not requiring supplemental oxygen - no longer requires ongoing medical care; • Not hospitalized, limitation on activities and/or requiring home oxygen; • Not hospitalized, no limitations on activities. 
Recovery is evaluated up until Day 29.

Key Secondary	

To evaluate the clinical efficacy of different investigational therapeutics relative to the control arm in adults hospitalized with COVID-19 according to clinical status (8-point ordinal scale) at Day 15
	
 • Death; • Hospitalized, on invasive mechanical ventilation or ECMO; • Hospitalized, on non-invasive ventilation or high flow oxygen devices; • Hospitalized, requiring supplemental oxygen; • Hospitalized, not requiring supplemental oxygen - requiring ongoing medical care (COVID-19 related or otherwise); • Hospitalized, not requiring supplemental oxygen - no longer requires ongoing medical care; • Not hospitalized, limitation on activities and/or requiring home oxygen; • Not hospitalized, no limitations on activities.
Additional Secondary	

1. To evaluate the clinical efficacy of different investigational therapeutics as compared to the control arm as assessed by:
 
 • Clinical Severity 
 ○ Ordinal scale: 
 ▪ Time to an improvement of one category and two categories from Day 1 (baseline) using an ordinal scale. 	
 • Clinical outcome assessed using ordinal scale daily while hospitalized and on Days 15, 22, and 29.

OBJECTIVES	ENDPOINTS (OUTCOME MEASURES)

 ▪ Subject clinical status using ordinal scale at Days 3, 5, 8, 11, 15, 22, and 29. ▪ Mean change in the ordinal scale from Day 1 to Days 3, 5, 8, 11, 15, 22, and 29. 	

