5.2 Exclusion Criteria

An individual who meets any of the following criteria will be excluded from participation in this study:

1. ALT or AST > 5 times the upper limit of normal.
2. Estimated glomerular filtration rate (eGFR) < 30 ml/min (including patients receiving hemodialysis or hemofiltration).
3. Pregnancy or breast feeding.
4. Anticipated discharge from the hospital or transfer to another hospital which is not a study site within 72 hours.
5. Allergy to any study medication.

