8.1.2.2 Ordinal Scale

The ordinal scale is the primary measure of clinical outcome.

The scale used in this study is as follows (from worst to best):

- Death;
- Hospitalized, on invasive mechanical ventilation or ECMO;
- Hospitalized, on non-invasive ventilation or high flow oxygen devices;
- Hospitalized, requiring supplemental oxygen;

- Hospitalized, not requiring supplemental oxygen - requiring ongoing medical care (COVID-19 related or otherwise);
- Hospitalized, not requiring supplemental oxygen - no longer requires ongoing medical care;
 - This would include those kept in hospital for quarantine/infection control, awaiting bed in rehabilitation facility or homecare, etc.
- Not hospitalized, limitation on activities and/or requiring home oxygen;
- Not hospitalized, no limitations on activities

To determine a subject's clinical status using the ordinal scale: On Day 1, report their clinical status at randomization. On Day 2, report the period from randomization to midnight on Day 1. On Day 3 through Day 11, or until discharged, and on Days 15, 22 and 29, provide the worst clinical assessment for the previous day (i.e., midnight to midnight; 00:00 – 23:59 (24-hr clock)). For example, on study Day 3 when completing the form, the worse clinical outcome measure of Day 2 is captured with the worst being death followed by ECMO, mechanical ventilation, etc. The Day 2 measurement is assessed as occurring anytime in that 24-hour period (00:00 to 23:59).

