9.2 Sample Size Determination

Primary endpoint: The log-rank test will be used to compare treatment arms with respect to time to recovery. For the log-rank test, the two key determinants of power are the total number of events (i.e., recoveries) E and the treatment-to-control ratio of the rate of recovery, R . The number of events required for power $1 - \beta$ to detect a recovery rate ratio of θ using a two-tailed test at $\alpha=0.05$ is approximately

$$E = \frac{4(1.96 + z_{\beta})^2}{\{\ln(\theta)\}^2},$$

where z_{β} is the $100(1 - \beta)$ th percentile of the standard normal distribution.

For 85% power, approximately 320 recoveries are required to detect a 40% increase in the rate of recovery ($\theta = 1.40$) from remdesivir. A recovery rate ratio of 1.40 is similar to, but slightly higher than the figure of 1.31 reported in Cao, Wang, Wen et al. (2020) for a lopinavir/ritonavir trial that used time to improvement by 2 categories as primary endpoint. A total of 400 recoveries is needed for a recovery ratio of 1.35 with 85% power. Table 4 provides power for various recovery rate ratios.

Table 4 Number of recoveries needed for 85% power assuming a type I error rate of 5% for various recovery ratios.

Recovery ratio (θ)	Number of recoveries needed for 85% power
1.25	723
1.30	523
1.35	400
1.40	318

Key secondary: A sample size can be computed using an (assumed) ordinal scale distribution for the placebo and the odds ratio representing clinical improvement. The odds ratio represents the odds of improvement in the ordinal scale for treatment relative to placebo [Whitehead, 1993]. The sample size to detect a given odds ratio for 1:1 randomization using a 2-tailed test at level α is given by

$$\frac{12(z_{\alpha/2} + z_{\beta})^2}{\lambda^2(1 - \sum_{i=1}^K p_i^3)}$$

where λ is the log odds ratio, p_i is the overall probability (combined over both arms) of being in the i th category of the K ordinal outcomes, and $z_{\alpha/2}$ and z_{β} are the $1 - \alpha/2$ and $1 - \beta$ quantiles of the standard normal distribution.

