9.4 Statistical Analyses

9.4.1 General Approach

This is a double-blind placebo controlled randomized trial testing a superiority hypothesis with a two-sided type I error rate of 5%. Secondary hypotheses have been ordered according to relative importance, with one key secondary hypothesis highlighted. These will be described according to the appropriate summary statistics (e.g., proportions for categorical data, means with 95% confidence intervals for continuous data, median for time-to-event data).

A statistical analysis plan will be developed and filed with the study sponsor prior to unblinding of study and database lock.

Unblinding of the study will occur after all subjects enrolled for 400 recoveries have reached the end of study, and these visits are monitored and data is cleaned.

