3.3.2. Recovery and Time to Recovery

The primary efficacy outcome measure is the time to recovery. Recovery will be defined as having a value of 1, 2, or 3 on the clinical status 8-point ordinal scale. The time to recovery will be defined as the elapsed time (in days) from randomization to the earliest day at which a subject reaches recovery. Note that since clinical status assessments are recorded as defined in Section 4.3, the day that is being assessed (not necessarily the day the response is collected) will be used to determine the timing of events. For example, a subject with a score of 5 recorded on Days 1 - 3 and a score of 3 recorded on Day 4 will have a time to recovery equal to 3 days. It is also possible that a subject has a clinical status score > 3 reported for a particular day but was subsequently discharged on the same day. For these scenarios where a subject is discharged with no reported clinical score of 1, 2, or 3 will be considered recovered at the time of discharge.

Any subjects that are lost to follow-up or terminated early prior to an observed recovery will be censored at the day of their last observed assessment. Subjects who complete follow-up but do not experience recovery will be censored at the day of their Day 29 visit. All deaths within Day 29 (and prior to recovery) will be considered censored at 28 days. Note that we do not expect many subjects to worsen after discharge.

However, we will evaluate whether any discharged subjects subsequently experience a worse clinical status and sensitivity analyses will be conducted accordingly. For these analyses, subjects who recover but are later re-admitted will not be considered a recovery but will instead be censored at 28 days. Sensitivity analyses will be performed where subjects who were crossover treated with remdesivir (per April 29, 2020 Protocol Administrative Letter) will be censored at the time of remdesivir treatment initiation. In addition, the analyses will be replicated where subjects who were unblinded, regardless of whether they received crossover treatment of remdesivir or not, will be censored at the time of unblinding.

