6.4. Covariates and Subgroups

Subgroup analyses for the main efficacy outcomes (i.e. the primary and key secondary analyses) will evaluate the treatment effect across the following subgroups:

- Geographic region:
 - US sites; Non-US sites
 - North American sites; Asian sites; European sites
- Duration of symptoms prior to enrollment
 - Quartiles
 - ≤ 10 days; > 10 days
 - \leq Median; $>$ Median
- Race (White; Black/African American; Asian; Other)
- Comorbidities
 - None; Any
 - None, One, Two or more
 - Obese; Non-Obese
- Age (<40 ; 40-64; 65 and older),
- Sex (Female; Male),

- Severity of disease
 - Randomization stratification: Mild/Moderate; Severe.
 - Actual disease severity at baseline: Mild/Moderate; Severe
 - Baseline ordinal scale category: 4; 5; 6; 7

Additionally, main analyses of all secondary outcomes will evaluate the treatment effect across the following subgroups:

- Duration of symptoms prior to enrollment (\leq Median; $>$ Median)
- Severity of disease
 - Randomization stratification: Mild/Moderate; Severe.
 - Actual disease severity at baseline: Mild/Moderate; Severe
 - Baseline ordinal scale category: 4; 5; 6; 7

The analyses of time to improvement will also be repeated in the subset of the randomized subjects who enrolled with a baseline clinical score of 7. As part of these analyses, the sensitivity analyses described in Section 3.3.4 regarding unblinded and retreated subjects will be performed in this subset, as well.

There will also be a sensitivity analysis of the primary, key secondary, and mortality outcomes to evaluate the effect of concomitant therapy including experimental treatment and off-label use of marketed medications that are intended as treatment for COVID-19 and are given to patient prior to and during the study. Subjects who report use of the following categories of therapies/treatments will be censored at the time of the earliest start date of any of the therapies/treatments:

- Protease inhibitors
- Polymerase inhibitors
- Other drugs used to treat COVID (off-label, experimental use)
- Corticosteroids
- Other anti-inflammatory drugs:
 - JAK inhibitors
 - Tyrosine kinase inhibitors
 - TNF inhibitors
 - Interleukin inhibitors
 - Interferons
 - Plasma
 - Immunoglobulins
 - T-cell therapies (anti-PD-1 monoclonal antibodies)

- Selective T-cell co-stimulation blockers
- B-cell therapies (CD 20 monoclonal antibodies)

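### Eligibility sets no floor on baseline clinical status, so a patient already in category 3 can be randomized and count as a primary recovery at time zero in either arm; the effect is dilution of unknown, probably small, size

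*Protocol*

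**What the plan says.** **Entry.** Inclusion 6 (Protocol 5.1, repeated in the synopsis and in SAP 4.2) needs one of four findings. The first is "Radiographic infiltrates by imaging (chest x-ray, CT scan, etc.), OR". The others are low oxygen saturation on room air, supplemental oxygen and mechanical ventilation. No criterion mentions the ordinal scale or a need for ongoing medical care. The exclusion closest to the point is "Anticipated discharge from the hospital or transfer to another hospital which is not a study site within 72 hours" (Protocol 5.2).

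**Category 3.** Protocol 8.1.2.2 describes this state, hospitalized without oxygen or further need for medical care, as follows: "This would include those kept in hospital for quarantine/infection control, awaiting bed in rehabilitation facility or homecare, etc". The Day 1 score is the status at randomization.

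**Endpoint.** Protocol 3 states: "Day of recovery is defined as the first day on which the subject satisfies one of the following three categories from the ordinal scale". Categories 1, 2 and 3 qualify. SAP 3.3.2 counts time "from randomization to the earliest day at which a subject reaches recovery" and has no rule for a subject who starts in category 3.

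**Analysis.** The baseline-status subgroups in SAP 6.4 are "Baseline ordinal scale category: 4; 5; 6; 7". The interim information fraction in SAP 6.6.2 is r/400, where r is the number of recoveries.

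**The concern.** Eligibility and the primary endpoint do not meet cleanly. A patient can pass every criterion while already in a state that the endpoint calls recovery. That event precedes any infusion, so it says nothing about treatment. It still enters the log-rank statistic, counts toward the 400 recoveries and raises r at the interim look.

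The subgroup list suggests that entry at category 4 or worse was intended, but a list of subgroups is not an entry rule. A category 3 subject would be in the primary analysis and in none of the four baseline-status subgroups.

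What is at stake is some loss of power, a rate ratio pulled toward 1, and an event count that overstates what is known about the treatment effect.

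**Working it through.** **1. Can such a patient enter?** Take an inpatient admitted with symptoms, PCR-positive on a sample under 72 hours old, with infiltrates, on room air, needing no further care, and expected to stay more than 72 hours for isolation or a rehabilitation bed.
- Inclusion 1 (admitted with symptoms): met.
- Inclusion 5 (recent positive PCR): met by its first branch.
- Inclusion 6: met by infiltrates alone.
- Exclusion 4: not triggered, because neither discharge nor transfer to a non-study hospital is expected within 72 hours.
- Day 1 score: 3, so the recovery definition is met at randomization. The worked example in SAP 3.3.2 leaves it unclear whether the recorded time would be 0 or 1 day. Either way it does not depend on arm.

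**2. Reproduce the design.** The inputs are two-sided alpha 0.05, 1:1 allocation and, from Protocol 9.2, "A total of 400 recoveries is needed for a recovery ratio of 1.35 with 85% power".
- Events: 4 × (1.96 + 1.036)² / (ln 1.35)² = 398.8, so 399 against the stated 400.
- Power with 400 events: drift = (ln 1.35 / 2) × √400 = 0.1501 × 20 = 3.00, and Φ(3.00 − 1.96) = 85.1%.
- Sample size: 400 / 0.70 = 571.4, so 572 as stated.

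**3. Add uninformative events.** Let f be the share of the 572 randomized who are in category 3 at baseline. The documents give no value, so f is an assumption. Each such subject is one of the 400 events, adding variance but no expected difference between arms:

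drift = (ln 1.35 / 2) × (400 − k) / √400, where k = 572 × f rounded to whole subjects.

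The diluted rate ratio is approximated by 1.35 raised to the power (400 − k)/400.

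| f | k | Drift | Power | Diluted rate ratio |
|---|---|---|---|---|
| 0 | 0 | 3.00 | 85.1% | 1.35 |
| 1% | 6 | 2.96 | 84.0% | 1.34 |
| 2% | 11 | 2.92 | 83.1% | 1.34 |
| 5% | 29 | 2.78 | 79.5% | 1.32 |

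**4. Check by simulation.** A stratified log-rank test using the SAP 8.1.1 formula was simulated with 572 subjects, 20% of them mild/moderate, with assumed hazards giving about 452 recoveries. Power was 89.2%, 85.8% and 83.3% with 0, 20 and 40 events placed at time zero in the mild/moderate stratum. The direction agrees. The event total differs, so the levels are not comparable with the table.

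**5. Larger enrolment.** Protocol 4.1 expects 600 to over 800 subjects. Assume 70% of all subjects recover, so E = 0.7N, with drift = 0.1501 × (E − fN)/√E.
- N = 600, E = 420: f = 2% gives 0.1501 × 408/20.49 = 2.99, power 85%; f = 5% gives 0.1501 × 390/20.49 = 2.86, power 81%.
- N = 700, E = 490: f = 5% gives 0.1501 × 455/22.14 = 3.08, power 87%.
- N = 800, E = 560: f = 5% gives 0.1501 × 520/23.66 = 3.30, power 91%.

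**6. Type I error.** Under the null, events at time zero fall between arms as randomization dictates. Observed minus expected has mean zero and the hypergeometric variance accounts for them, so the test keeps its size.

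**The case against.** The strongest reply is that this is an edge case the plan would largely reveal.

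- **Entry is narrower than Inclusion 6 suggests.** If the positive sample is 72 hours old or more, Inclusion 5 also requires progressive disease. That removes much of the typical isolation-only group, who were tested earlier and have since improved. Exclusion 4 removes those expected to leave soon. Category 4 covers care for any reason, so many newly diagnosed inpatients would score 4. All of this stands. It shrinks the group without closing the gap.
- **Such subjects would be visible.** A reader might infer from the subgroup list that the SAP treats baseline category 3 as impossible. The table shells do not support that: Table 34 has a Day 1 row for category 3, and Table 49 leaves room for other baseline scores.
- **Clean estimates exist in part.** Time to recovery is already analysed within baseline categories 4, 5, 6 and 7 (SAP 6.4 and 8.1.2). None of these can contain a category 3 subject, but no pooled estimate across the four is planned.
- **Power may be offset.** Enrolment beyond 572, and the SAP's use of both an early and a full analysis set, can restore power. Protocol 9.3, however, ties the primary analysis to the subjects enrolled to reach 400 recoveries.
- **Timing.** SAP version 3.0 was written after the interim results went to the DSMB, and enrolment was permitted only to April 20, 2020. An entry criterion cannot help subjects already randomized. This stands and limits the remedy for the current comparison.

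**Conclusion.** The gap is real on the text: a patient can be randomized with the primary endpoint already met, and following the plan exactly would count that as a recovery. The consequence is dilution toward the null and overstated information. At 572 subjects and 400 recoveries, the cost is about 1 point of power if 1% of subjects are affected, 2 points at 2% and between 5 and 6 points at 5%. These figures rest on the assumed f, a true rate ratio of 1.35 in all other subjects, and a simple drift approximation.

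A reader might infer that the trial is materially underpowered or its false-positive rate inflated. The documents support neither. They give no count of such patients, two criteria limit the number, expected enrolment exceeds 572, and the null behaviour of the test is unaffected. The sample-size arithmetic is not in error.

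A reader might also infer that these subjects should be removed from r at the interim look. That would be unsound. If they remain events in the ITT log-rank test they still contribute to its variance, so a reduced r/400 would no longer match the statistic, and that look is complete.

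**What to change.** **Prospectively, including later stages of the adaptive protocol.** In Protocol 1.1 and 5.1 and SAP 4.2, require ordinal category 4, 5, 6 or 7 at randomization, using the Day 1 score already recorded.

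**For the current comparison.**
- State in SAP 3.3.2 that a subject in category 3 at baseline stays in the ITT primary analysis as randomized.
- Report the number of such subjects by arm.
- Add to SAP 8.1.2 a pooled, severity-stratified time-to-recovery sensitivity analysis restricted to baseline categories 4 to 7.
- Leave r/400 at the completed interim look unchanged.

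**Cost.** A few isolation-only inpatients become ineligible. The entry line needs a protocol amendment with IRB approval across up to about 100 sites. The analysis change is one table row and needs no new data.
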